Attachment 5: Response Evaluation Criteria in Solid Tumors (RECIST) Quick Reference

RECIST version 1.1	
Measurable Tumor Burden	A maximum of 5 target lesions in total (and up to 2 per organ) can be identified at baseline and measured through the course of therapy.
Minimum Size of Measurable Lesions	
≥10 mm in longest diameter (LD) by CT scan of which slice is thickness no greater than 5 mm
 
≥15 mm in short axis (SA) for nodal lesions by CT scan of which slice is thickness no greater than 5 mm
 
≥10 mm in LD for clinical lesions (must be measured using electronic calipers)
 
≥20 mm in LD for chest X-ray (if clearly defined and surrounded by aerated lung); CT is preferable
 
Ultrasound (US) cannot be used to measure lesions

Lymph Nodes	
Lymph nodes are considered pathologically enlarged if >10 mm in SA.
 
To be measurable, nodal lesions must be ≥15 mm in SA by CT scan of which slice is thickness no greater than 5 mm.
 
Nodal lesions with SA >10 mm and <15 mm are non-measurable.
 
The sum of the diameters (LD for non-nodal target lesions, SA for nodal lesions) is followed through the course of therapy.

Bone Lesions	
A lytic or mixed lytic-blastic bone lesion with a soft tissue component assessed on CT/MRI can be measurable if the minimum size criteria are met.
 
Blastic bone lesions and bone lesions assessed on bone scan, positron emission therapy (PET) or plain films are non-measurable.

Cystic Lesions	
Lesions that meet the criteria for radiographically defined simple cysts are not malignant.
 
Cystic lesions thought to be metastases can be measurable if they meet the minimum size criteria.
 
If noncystic lesions are present in the same patient, they are preferred for selection as target lesions.

Lesions with Prior Local Treatment	Lesions in previously irradiated areas (or areas treated with local therapy) are not measurable unless the lesion has progressed since therapy.
Too Small To Measure	If a target lesion becomes too small to measure, a default value of 5 mm is assigned. If the lesion disappears, the measurement is recorded as 0 mm.
Lesions which split or Coalesce	
If non-nodal target lesions fragment, the LDs of the fragmented portions are added to calculate the sum.
 
If target lesions coalesce and cannot be distinguished, the LD of the coalesced lesion is added to the sum.

Definition of Complete Response (CR)	
CR requires:
 
 • The disappearance of all lesions. • All lymph nodes must be non-pathological in size (<10 mm SA). • Normalization of tumor marker level.
Definition of Partial Response (PR)	≥30% decrease in the sum of the diameters of all target lesions compared with baseline, in absence of new lesions or unequivocal progression of non-target lesions
Definition of Stable Disease (SD)	<30% decrease in sum of diameters of all target lesions compared with baseline and <20% increase compared with nadir, in the absence of new lesions or unequivocal progression of nontarget lesions

Definition of Progressive Disease (PD)	PD is assessed if the sum of the diameters has increased by $\geq 20\%$ and ≥ 5 mm from nadir (including baseline if it is the smallest sum). Patients with measurable disease: for "unequivocal progression" based on nontarget disease, there must be an overall level of substantial worsening that merits discontinuation of therapy (if target disease is SD/PR). Patients without measurable disease: for "unequivocal progression" of non-target disease, the increase in overall tumor burden must be comparable to the increase required for PD of measurable disease. Furthermore, the appearance of 1 or more new lesions or unequivocal progression of a nontarget lesion is also considered as PD.
Assessment of New Lesions	New lesions should be unequivocal and not attributable to differences in scanning technique or findings which may not be tumor (ie, 'new' bone lesions may be healing or flare of pre-existing lesions). If one is equivocal, repeat scans are needed to confirm. If confirmed, PD is assessed at the date of the initial scan. Lesions identified in anatomic locations not scanned at baseline are considered new. New lesions on US should be confirmed on CT/MRI.
FDG-PET	New lesions can be assessed using FDG-PET: (-) PET at baseline and (+) PET at follow-up is PD based on a new lesion. No PET at baseline and (+) PET at follow-up is PD if the new lesion is confirmed on CT. If a subsequent CT confirms the new lesion, the date of the PD is the date of the initial PET scan. No PET at baseline and (+) PET at follow-up corresponding to pre-existing lesion on CT that is not progressing; not PD.
Recurrence of lesions	For a patient with SD/PR, a lesion which disappears and then reappears will continue to be measured and added to the sum. Response will depend upon the status of the other lesions. For a patient with CR, reappearance of a lesion would be considered PD.
Overall Response	One overall response table integrates target, nontarget, and new lesions for subjects with measurable disease; and another table integrates nontarget and new lesions for subjects without measurable disease.
Confirmation of Response	In nonrandomized trials where response is the primary endpoint, confirmation of PR and CR is required to ensure responses identified are not the result of measurement error. In these trials, subsequent confirmation of PR with one interim time point of SD is acceptable. In randomized trials, confirmation of response is not required.
CR=complete response, CT=computed tomography, FDG-PET=fluorodeoxyglucose positron emission therapy LD=longest diameter, PD=progressive disease, PR=partial response, SA=short axis, SD=stable disease, US=ultrasound	

Source: Eisenhauer 2009¹⁴

Attachment 6: Immune-related Response Evaluation Criteria in Solid Tumors (irRECIST)

	RECIST 1.1	irRECIST
New, measurable lesions	Always represent progressive disease (PD)	Incorporated into tumor burden
New, non-measurable lesions	If unequivocal, represent PD; if equivocal, does not represent PD (but precludes complete response) and should be followed for unequivocal progression at a later timepoint	Same as RECIST 1.1.
Non-target lesions	Changes contribute to defining best overall response (BOR) of CR, PR, SD, and PD	Same as RECIST 1.1.
Response Category		
CR	Disappearance of all lesions	Same as RECIST 1.1.
PR	≥30% decrease in the sum of the diameters of all target lesions compared with baseline, in absence of new lesions or unequivocal progression of non-target lesions	Same as RECIST 1.1.
SD	<30% decrease in sum of diameters of all target lesions compared with baseline and <20% increase compared with nadir, in the absence of new lesions or unequivocal progression of nontarget lesions	Same as RECIST 1.1.
PD	At least 20% increase in the sum of the diameters for target lesions and/or unequivocal progression of nontarget lesions, compared with nadir (at any single time point including baseline). The sum must also demonstrate an absolute increase of at least 5 mm.	Same as RECIST 1.1, with the following exceptions: 1. Increases are observed in 2 consecutive observations at least 4 weeks apart. 2. New target lesions (maximum of 5 new target lesions; maximum of 2 per organ) are included in calculating tumor burden
Handling of lymph nodes	Lymph nodes are considered pathologically enlarged if >10 mm in SA. To be measurable, nodal lesions must be ≥15 mm in SA. Nodal lesions with SA >10 mm and <15 mm are non-measurable. The sum of the diameters (LD for non-nodal target lesions, SA for nodal lesions) is followed through the course of therapy.	Same as RECIST 1.1.
BOR=best overall response, CR=complete response, LD=longest diameter, PD=progressive disease, PR=partial response, SA=short axis, SD=stable disease		

Sources: Henze 2016¹⁹, Nishino 2013³³

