2.1.2. Endpoints

Primary Endpoint

- The primary endpoint is ORR: the proportion of subjects with a partial response (PR) or complete response (CR) as defined by RECIST 1.1

Secondary Endpoints

- Incidence of adverse events
- DoR: the duration from the date of the initial documentation of a response to the date of the first objectively documented evidence of recurrence or progressive disease or death, whichever status is recorded first.
- CBR: the proportion of subjects who achieve disease control (CR, PR, or SD with duration of at least 16 weeks).
- PFS: the duration from the date of randomization to the date of objectively documented progression or death due to any cause, whichever status is recorded first.
- OS: the duration from the date of randomization to the date of death due to any cause.
- Serum daratumumab concentration (C_{min} , C_{max}) and incidence of anti-daratumumab antibodies
- Serum atezolizumab concentration (C_{min} , C_{max}) and incidence of anti-atezolizumab antibodies

Exploratory Endpoints

- ORR_i: the proportion of subjects with a partial response (PR) or complete response (CR) evaluated by irRECIST
- ORR, DoR, CBR, incidence of adverse events, daratumumab and atezolizumab serum concentration and incidence of anti-daratumumab antibodies and anti-atezolizumab antibodies

Refer to Section 9, Study Evaluations for evaluations related to endpoints.

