9.4.1. Disease Assessments

Screening Tumor Assessments

Screening tumor assessments will include CT scans (with IV contrast unless contraindicated) or MRIs of the chest, abdomen, head, and pelvis. For subjects with known bone lesions, CT, or MRI scan of the affected area of bone will be required at Screening. Additionally, CT scans of the neck should also be performed at Screening if clinically indicated. Subjects who are intolerant to IV contrast agents or in whom IV contrast is contraindicated may have CT scans performed with oral contrast; the reason for not using IV contrast must be noted in the source documents. At the investigator's discretion, other methods of assessment of measurable disease (eg, physical examination) as per RECIST 1.1 may be used.

Magnetic resonance imaging may be used to evaluate sites of disease that cannot be adequately imaged using CT or if IV and oral contrast for CT scan are contraindicated. In any case where an MRI is performed, it must be the imaging technique used to assess disease at Screening and at all subsequent response evaluations.

Tumor assessments performed as standard of care prior to obtaining informed consent and within 28 days of Cycle 1, Day 1 may be used rather than repeating tests. All known sites of active disease must be documented at Screening.

Subsequent Tumor Assessments

At each subsequent tumor evaluation, chest and abdomen CT scans or MRIs, in addition to any other known sites of active disease, will be performed. The same radiographic procedure used to assess disease sites at Screening should be used throughout the study (eg, the same contrast protocol for CT scans). Response will be assessed by the investigator using RECIST 1.1; irRECIST will also be used for exploratory purposes.

Deterioration of health status requiring discontinuation of study treatment without objective evidence of progressive disease should be reported as "clinical disease progression". Every effort should be made to document objective progression via radiographic confirmation.

Subjects in Arm A who crossed over to Arm B after confirmed disease progression should be carefully evaluated to determine whether they will benefit from treatment with atezolizumab monotherapy.

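### Attachment 6 adds new measurable lesions to irRECIST tumour burden but its irRECIST PR and SD definitions exclude them, so some subjects have no category and some partial responses drop out of the exploratory ORRi

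*Protocol*

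**What the plan says.** Protocol Section 2.1.2 defines ORRi, an exploratory endpoint, as "the proportion of subjects with a partial response (PR) or complete response (CR) evaluated by irRECIST". Section 9.4.1 makes RECIST 1.1 the criterion for investigator assessment and adds that "irRECIST will also be used for exploratory purposes".

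Attachment 6 sets the two systems side by side. For new measurable lesions, the RECIST 1.1 column makes them progression in every case, while the irRECIST column has them "Incorporated into tumor burden". The irRECIST PD cell adopts RECIST 1.1 with two listed exceptions:

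- "Increases are observed in 2 consecutive observations at least 4 weeks apart"
- New target lesions, within a stated maximum number, "are included in calculating tumor burden".

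The irRECIST PR and SD cells adopt RECIST 1.1 with no exceptions listed. The RECIST 1.1 PR cell beside them applies "in absence of new lesions or unequivocal progression of non-target lesions", and the SD cell applies "in the absence of new lesions or unequivocal progression of nontarget lesions". New non-measurable lesions are handled as in RECIST 1.1 in both columns.

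SAP Section 1.1 lists the comparison of ORR by irRECIST as an exploratory objective. SAP Section 5 gives no irRECIST definition, derivation or analysis.

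**The concern.** Two rows of the table count a new measurable lesion as part of the burden to be measured. Two other rows treat its mere presence as disqualifying. A new measurable lesion therefore no longer makes the subject PD, yet it still prevents the subject from being PR or SD. If the total burden has not risen enough for PD, no category is left.

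Incorporating new measurable lesions is one of only two substantive ways in which irRECIST departs from RECIST 1.1 in this attachment, and for PR it is cancelled. Responses are assessed by investigators at multiple sites in an open-label trial. Different readers could apply different rules, or a programmer could have to choose one after the data have been seen.

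**Working it through.** No stated figure needs reproducing; the check is whether the categories in Attachment 6 cover every subject. The size rules come from the attachment, with new lesions treated in two ways.

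**Rules**
- PR: sum at most 0.70 × baseline.
- SD: sum above 0.70 × baseline and below 1.20 × nadir.
- PD: sum at least 1.20 × nadir and at least 5 mm above nadir, seen twice at least 4 weeks apart for irRECIST.
- CR: no lesions remaining.

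**Readings**
- As written: PR and SD use the target sum and require no new lesion; PD uses targets plus new measurable lesions.
- Burden reading: every category uses targets plus new measurable lesions, and PR and SD carry no bar on new measurable lesions.

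**Examples.** These values are illustrative assumptions, not trial data. With baseline and nadir both 100 mm, the PR limit is 0.70 × 100 = 70 mm and the PD limit is 1.20 × 100 = 120 mm.

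| Case | Targets (mm) | New measurable lesion (mm) | Total (mm) | Change | As written | Burden reading |
|---|---|---|---|---|---|---|
| A | 50 | 12 | 62 | −38% | none | PR |
| B | 85 | 12 | 97 | −3% | none | SD |
| C, first scan | 130 | 0 | 130 | +30% | PD only if confirmed | PD only if confirmed |
| C, next scan | 60 | 0 | 60 | −40% | PR | PR |

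- **Case A, as written.** It is not CR because lesions remain. It is not PR: 50 is below 70, but a new lesion is present. It is not SD: the targets fell by 50%, and a new lesion is present. It is not PD because 62 is below 120.
- **Case B, as written.** It meets the size condition for SD (a 15% fall in targets) but fails on the new lesion. It is not PD because 97 is below 120.
- **Case C.** The rise to 130 mm is not confirmed, so it is not irRECIST PD, and the later PR counts under either reading.

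**Effect on ORRi.** Only CR and PR enter ORRi, so case A is lost from it and case B is not relevant to it. If an unclassified subject were put in the not-evaluable category of SAP Section 5.2, that subject would still not be a responder. At the third DMC review there were 88 subjects, 44 per arm, so one such subject shifts an arm's ORRi by 1/44 = 2.3 percentage points.

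**The case against.** The best defence is that the new-measurable-lesion row stands above the response categories and states a general rule for irRECIST, so it governs the sum used in the rows below. The attachment is also a summary that cites two publications for the full criteria. This reading is possible, but the layout tells against it: the PD cell spells out its exceptions to RECIST 1.1, and the PR and SD cells spell out none. The SAP does not help. Its reference list cites a 2009 guideline on immune-related response criteria rather than the two sources named under Attachment 6.

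Several limits on the point do stand, and they rule out stronger readings that a reader might infer.

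- **That ORRi cannot capture atypical response at all.** Protocol Sections 9.4.2 and 9.6 describe a transient flare, or apparent progression with growth in tumour size, followed by response. The confirmation requirement for irRECIST PD captures that pattern, as case C shows.
- **That every response accompanied by a new measurable lesion is lost.** A PR recorded before the lesion appears still counts. So does a PR at a later scan when the lesion has resolved and the targets are still down by at least 30%. CR is unaffected.
- **That the 8 to 10% in Protocol Section 9.6 gives the number lost.** That figure concerns apparent progression with increased tumour size on PD-1 inhibitors. It is not a rate of response with new measurable lesions, and multiplying it by the arm size does not estimate this problem.
- **That the SD conflict biases ORRi.** It leaves subjects unclassified, but SD is not part of ORRi.

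It is also fair to say that imaging after RECIST 1.1 progression was conditional (Protocol Sections 9.4 and 9.4.2, Table 12). Some such responses would have gone unobserved whatever the wording.

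**Conclusion.** The point holds as a contradiction within Attachment 6. As written, a subject with a new measurable lesion and a total burden that is falling or stable has no irRECIST category at that scan. A partial response seen only while a new measurable lesion is present is missing from ORRi.

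Its size is limited. ORRi is exploratory, and no alpha, sample size or stated decision rule depends on it. The primary RECIST 1.1 ORR is unaffected. The number of subjects concerned cannot be estimated from the documents; it could be none. The conclusion assumes only that the irRECIST PR and SD cells mean what they say, namely that RECIST 1.1 applies there without exception. It is still worth correcting, because the two readings give different categories for the same scan and nothing in the SAP chooses between them.

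**What to change.** Reconcile the rows of Attachment 6 by rewriting two irRECIST cells:

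- **PR:** a decrease from baseline of at least 30% in the total of target plus new measurable lesions.
- **SD:** the corresponding rule on the same total.
- **Both:** a new measurable lesion alone does not preclude the category. The maximum number of new lesions already set in the PD row applies, and the handling of new non-measurable lesions is unchanged.

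Put the same derivation of ORRi in the SAP before ORRi is tabulated. Enrolment is closed, Amendment 7 describes the clinical database as locked, and the CSR is to use the data from the third DMC review (Protocol Sections 3.2 and 17.9.1). The practical step is therefore to apply the rule to the lesion measurements already collected, to say in the CSR when the rule was fixed, and to list the subjects whose category differs between the two readings. That list would also supply the size that the documents cannot.

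The cost is two table cells and one derivation. It assumes that diameters of new measurable lesions were recorded, as the burden calculation in Attachment 6 requires. Where they were not, the CSR should report this as a limitation of ORRi.

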Attachment 7: Management Guidelines for Atezolizumab

Management guidelines for toxicities associated or possibly associated with atezolizumab are provided as follows:

- Pulmonary events, please see [Table 13](#)
- Hepatic events, please see [Table 14](#)
- Gastrointestinal events, please see [Table 15](#)
- Endocrine events, please see [Table 16](#)
- Ocular events, please see [Table 17](#)
- Pancreatic events, please see [Table 18](#)
- Immune-mediated myocarditis, please see [Table 19](#)
- Dermatologic events, please see [Table 20](#)
- Neurologic disorders and meningoencephalitis, please see [Table 21](#)
- Systemic immune activation events, please see [Table 22](#)
- Immune-related Nephritis, please see [Table 23](#).

Table 13: Management Guidelines for Pulmonary Events, Including Pneumonitis

Event	Management
Pulmonary event, Grade 1	
 • Continue atezolizumab and monitor closely. • Re-evaluate on serial imaging. • Consider subject referral to pulmonary specialist.
Pulmonary event, Grade 2	
 • Withhold atezolizumab for up to 12 weeks after event onset.^a • Refer subject to pulmonary and infectious disease specialists and consider bronchoscopy or BAL. • Initiate treatment with 1–2 mg/kg/day oral prednisone or equivalent. • If event resolves to Grade 1 or better, resume atezolizumab.^b • If event does not resolve to Grade 1 or better while withholding atezolizumab, permanently discontinue atezolizumab and contact Sponsor.^c
Pulmonary event, Grade 3 or Grade 4	
 • Permanently discontinue atezolizumab and contact the Sponsor.^c • Bronchoscopy or BAL is recommended. • Initiate treatment with 1–2 mg/kg/day oral prednisone or equivalent. • If event does not improve within 48 hours after initiating corticosteroids, consider adding an immunosuppressive agent. • If event resolves to Grade 1 or better, taper corticosteroids over ≥ 1 month.

BAL=bronchoscopic alveolar lavage; IVIG=intravenous immunoglobulin

- Atezolizumab may be withheld for a longer period of time (ie, >12 weeks after event onset) to allow for corticosteroids (if initiated) to be reduced to ≤ 10 mg/day oral prednisone or equivalent. The acceptable length of the extended period of time must be agreed upon by the investigator and the Sponsor.
- If corticosteroids have been initiated, they must be tapered over ≥ 1 month to ≤ 10 mg/day oral prednisone or equivalent before atezolizumab can be resumed.
- Resumption of atezolizumab may be considered in subjects who are deriving benefit and have fully recovered from the immune-related event. Subjects can be rechallenged with atezolizumab only after approval has been documented by both the investigator (or an appropriate delegate) and the Sponsor.

Table 14: Management Guidelines for Hepatic Events

Event	Management
Hepatic event, Grade 1	
 • Continue atezolizumab. • Monitor LFTs until values resolve to within normal limits.
Hepatic event, Grade 2	
All events:
 
 • Monitor LFTs more frequently until return to baseline values. 
Events of >5 days' duration:
 
 • Withhold atezolizumab for up to 12 weeks after event onset.^a • Initiate treatment with 1–2 mg/kg/day oral prednisone or equivalent. • If event resolves to Grade 1 or better, resume atezolizumab.^b • If event does not resolve to Grade 1 or better while withholding atezolizumab, permanently discontinue atezolizumab and contact
Hepatic event, Grade 3 or 4	
 • Permanently discontinue atezolizumab and contact the Sponsor.^c • Consider subject referral to gastrointestinal specialist for evaluation and liver biopsy to establish etiology of hepatic injury. • Initiate treatment with 1–2 mg/kg/day oral prednisone or equivalent. • If event does not improve within 48 hours after initiating corticosteroids, consider adding an immunosuppressive agent. • If event resolves to Grade 1 or better, taper corticosteroids over ≥ 1 month.

LFT= liver function tests.

- Atezolizumab may be withheld for a longer period of time (ie, > 12 weeks after event onset) to allow for corticosteroids (if initiated) to be reduced to ≤ 10 mg/day oral prednisone or equivalent. The acceptable length of the extended period of time must be agreed upon by the investigator and the Sponsor.
- If corticosteroids have been initiated, they must be tapered over ≥ 1 month to ≤ 10 mg/day oral prednisone or equivalent before atezolizumab can be resumed.
- Resumption of atezolizumab may be considered in subjects who are deriving benefit and have fully recovered from the immune-related event. Subjects can be rechallenged with atezolizumab only after approval has been documented by both the investigator (or an appropriate delegate) and the Sponsor.

Table 15: Management Guidelines for Gastrointestinal Events (Diarrhea or Colitis)

Event	Management
Diarrhea or colitis, Grade 1	
 • Continue atezolizumab. • Initiate symptomatic treatment. • Endoscopy is recommended if symptoms persist for >7 days. • Monitor closely.
Diarrhea or colitis, Grade 2	
 • Withhold atezolizumab for up to 12 weeks after event onset. ^a • Initiate symptomatic treatment. • Subject referral to GI specialist is recommended. • For recurrent events or events that persist > 5 days, initiate treatment with 1–2 mg/kg/day oral prednisone or equivalent. • If event resolves to Grade 1 or better, resume atezolizumab. ^b • If event does not resolve to Grade 1 or better while withholding atezolizumab, permanently discontinue atezolizumab and contact Sponsor. ^c
Diarrhea or colitis, Grade 3	
 • Withhold atezolizumab for up to 12 weeks after event onset. ^a • Refer subject to gastrointestinal specialist for evaluation and confirmatory biopsy. • Initiate treatment with 1–2 mg/kg/day IV methylprednisolone or equivalent and convert to 1–2 mg/kg/day oral prednisone or equivalent upon improvement. • If event resolves to Grade 1 or better, resume atezolizumab. ^b • If event does not resolve to Grade 1 or better while withholding atezolizumab, permanently discontinue atezolizumab and contact Sponsor. ^c
Diarrhea or colitis, Grade 4	
 • Permanently discontinue atezolizumab and contact the Sponsor. ^c • Refer subject to gastrointestinal specialist for evaluation and confirmation biopsy. • Initiate treatment with 1-2 mg/kg/day IV methylprednisolone or equivalent and convert to 1-2 mg/kg/day oral prednisone or equivalent upon improvement. • If event does not improve within 48 hours after initiating corticosteroids, consider adding an immunosuppressive agent.

a. Atezolizumab may be withheld for a longer period of time (ie, >12 weeks after event onset) to allow for corticosteroids (if initiated) to be reduced to ≤10 mg/day oral prednisone or equivalent. The acceptable length of the extended period of time must be agreed upon by the investigator and the Sponsor.

b. If corticosteroids have been initiated, they must be tapered over ≥1 month to ≤10 mg/day oral prednisone or equivalent before atezolizumab can be resumed.

c. Resumption of atezolizumab may be considered in subjects who are deriving benefit and have fully recovered from the immune-related event. Subjects can be rechallenged with atezolizumab only after approval has been documented by both the investigator (or an appropriate delegate) and the Sponsor.

Table 16: Management Guidelines for Endocrine Events

Event	Management
Asymptomatic hypothyroidism	
 • Continue atezolizumab. • Initiate treatment with thyroid replacement hormone. • Monitor TSH weekly.
Symptomatic hypothyroidism	
 • Withhold atezolizumab. • Initiate treatment with thyroid replacement hormone. • Monitor TSH weekly. • Consider subject referral to endocrinologist. • Resume atezolizumab when symptoms are controlled and thyroid function is improving.
Asymptomatic hyperthyroidism	
TSH ≥ 0.1 mU/L and < 0.5 mU/L:
 
 • Continue atezolizumab. • Monitor TSH every 4 weeks. 
TSH < 0.1 mU/L:
 
 • Follow guidelines for symptomatic hyperthyroidism.
Symptomatic hyperthyroidism	
 • Withhold atezolizumab. • Initiate treatment with anti-thyroid drug such as methimazole or carbimazole as needed. • Consider subject referral to endocrinologist. • Resume atezolizumab when symptoms are controlled and thyroid function is improving. • Permanently discontinue atezolizumab and contact the Sponsor for life-threatening immune-related hyperthyroidism.^a
Symptomatic adrenal insufficiency, Grade 2-4	
 • Withhold atezolizumab for up to 12 weeks after event onset.^b • Refer subject to endocrinologist. • Perform appropriate imaging. • Initiate treatment with 1–2 mg/kg/day IV methylprednisolone or equivalent and convert to 1–2 mg/kg/day oral prednisone or equivalent upon improvement. • If event resolves to Grade 1 or better, resume atezolizumab.^c • If event does not resolve to Grade 1 or better while withholding atezolizumab, permanently discontinue atezolizumab and contact Sponsor.^a
Hyperglycemia, Grade 1 or 2	
 • Continue atezolizumab. • Initiate treatment with insulin if needed. • Monitor for glucose control.
Hyperglycemia, Grade 3 or 4	
 • Withhold atezolizumab. • Initiate treatment with insulin. • Monitor for glucose control. • Resume atezolizumab when symptoms resolve and glucose levels are stable.

Hypophysitis pan-hypopituitarism), Grade 2-3	
 • Withhold atezolizumab for up to 12 weeks after event onset.^b • Refer subject to endocrinologist. • Perform brain MRI (pituitary protocol). • Initiate treatment with 1-2 mg/kg/day IV methylprednisolone or equivalent and convert to 1-2 mg/kg/day oral prednisone or equivalent upon improvement. • If event resolves to Grade 1 or better, resume atezolizumab.^c • If event does not resolve to Grade 1 or better while withholding atezolizumab, permanently discontinue atezolizumab and contact Sponsor.^a • For recurrent hypophysitis, treat as a Grade 4 event.
Hypophysitis pan-hypopituitarism), Grade 4	
 • Permanently discontinue atezolizumab and contact the Sponsor.^a • Refer subject to endocrinologist. • Perform brain MRI (pituitary protocol). • Initiate treatment with 1-2 mg/kg/day IV methylprednisolone or equivalent and convert to 1-2 mg/kg/day oral prednisone or equivalent upon improvement.^b • Initiate hormone replacement therapy if clinically indicated.

TSH=thyroid-stimulating hormone

- a. Resumption of atezolizumab may be considered in subjects who are deriving benefit and have fully recovered from the immune-related event. Subjects can be rechallenged with atezolizumab only after approval has been documented by both the investigator (or an appropriate delegate) and the Sponsor.
- b. Atezolizumab may be withheld for a longer period of time (ie, >12 weeks after event onset) to allow for corticosteroids (if initiated) to be reduced to ≤ 10 mg/day oral prednisone or equivalent. The acceptable length of the extended period of time must be agreed upon by the investigator and the Sponsor.
- c. If corticosteroids have been initiated, they must be tapered over ≥ 1 month to ≤ 10 mg/day oral prednisone or equivalent before atezolizumab can be resumed.

Table 17: Management Guidelines for Ocular Events

Event	Management
Ocular event, Grade 1	
 • Continue atezolizumab. • Subject referral to ophthalmologist is strongly recommended. • Initiate treatment with topical corticosteroid eye drops and topical immunosuppressive therapy. • If symptoms persist, treat as a Grade 2 event.
Ocular event, Grade 2	
 • Withhold atezolizumab for up to 12 weeks after event onset.^b • Subject referral to ophthalmologist is strongly recommended. • Initiate treatment with topical corticosteroid eye drops and topical immunosuppressive therapy. • If event resolves to Grade 1 or better, resume atezolizumab.^a • If event does not resolve to Grade 1 or better while withholding atezolizumab, permanently discontinue atezolizumab and contact Sponsor.^c
Ocular event, Grade 3 or 4	
 • Permanently discontinue atezolizumab and contact the Sponsor.^c • Refer subject to ophthalmologist. • Initiate treatment with 1–2 mg/kg/day oral prednisone or equivalent. • If event resolves to Grade 1 or better, taper corticosteroids over ≥ 1 month.

a. If corticosteroids have been initiated, they must be tapered over ≥ 1 month to ≤ 10 mg/day oral prednisone or equivalent before atezolizumab can be resumed.

b. Atezolizumab may be withheld for a longer period of time (ie, >12 weeks after event onset) to allow for corticosteroids (if initiated) to be reduced to ≤ 10 mg/day oral prednisone or equivalent. The acceptable length of the extended period of time must be agreed upon by the investigator and the Sponsor.

c. Resumption of atezolizumab may be considered in subjects who are deriving benefit and have fully recovered from the immune-related event. Subjects can be rechallenged with atezolizumab only after approval has been documented by both the investigator (or an appropriate delegate) and the Sponsor.

Table 18: Management Guidelines for Pancreatic Events, Including Pancreatitis

Event	Management
Amylase and/or lipase elevation, Grade 2	
 • Continue atezolizumab. • Monitor amylase and lipase weekly. • For prolonged elevation (eg, > 3 weeks), consider treatment with 10 mg/day oral prednisone or equivalent.
Amylase and/or lipase elevation, Grade 3 or 4	
 • Withhold atezolizumab for up to 12 weeks after event onset.^a • Refer subject to gastrointestinal specialist. • Monitor amylase and lipase every other day. • If no improvement, consider treatment with 1–2 mg/kg/day oral prednisone or equivalent. • If event resolves to Grade 1 or better, resume atezolizumab.^b • If event does not resolve to Grade 1 or better while withholding atezolizumab, permanently discontinue atezolizumab and contact Sponsor.^c • For recurrent events, permanently discontinue atezolizumab and contact the Sponsor.^c
Immune-related pancreatitis, Grade 2 or 3	
 • Withhold atezolizumab for up to 12 weeks after event onset.^a • Refer subject to gastrointestinal specialist. • Initiate treatment with 1–2 mg/kg/day intravenous methylprednisolone or equivalent and convert to 1–2 mg/kg/day oral prednisone or equivalent upon improvement. • If event resolves to Grade 1 or better, resume atezolizumab.^b • If event does not resolve to Grade 1 or better while withholding atezolizumab, permanently discontinue atezolizumab and contact Sponsor.^c • For recurrent events, permanently discontinue atezolizumab and contact the Sponsor.^c
Immune-related pancreatitis, Grade 4	
 • Permanently discontinue atezolizumab and contact the Sponsor.^c • Refer subject to gastrointestinal specialist. • Initiate treatment with 1–2 mg/kg/day intravenous methylprednisolone or equivalent and convert to 1–2 mg/kg/day oral prednisone or equivalent upon improvement. • If event does not improve within 48 hours after initiating corticosteroids, consider adding an immunosuppressive agent. • If event resolves to Grade 1 or better, taper corticosteroids over ≥ 1 month.

a. Atezolizumab may be withheld for a longer period of time (ie, >12 weeks after event onset) to allow for corticosteroids (if initiated) to be reduced to ≤ 10 mg/day oral prednisone or equivalent. The acceptable length of the extended period of time must be agreed upon by the investigator and the Sponsor.

b. If corticosteroids have been initiated, they must be tapered over ≥ 1 month to ≤ 10 mg/day oral prednisone or equivalent before atezolizumab can be resumed.

c. Resumption of atezolizumab may be considered in subjects who are deriving benefit and have fully recovered from the immune-related event. Subjects can be rechallenged with atezolizumab only after approval has been documented by both the investigator (or an appropriate delegate) and the Sponsor.

Table 19: Management Guidelines for Immune-Related Myocarditis

Event	Management
Immune-related myocarditis, Grade 1	
 • Refer subject to cardiologist • Initiate treatment as per institutional guidelines.
Immune-related myocarditis, Grade 2	
 • Withhold atezolizumab for up to 12 weeks after event onset^a and contact Sponsor. • Refer subject to cardiologist • Initiate treatment as per institutional guidelines and consider antiarrhythmic drugs, temporary pacemaker, ECMO, or VAD as appropriate. • Consider treatment with 1-2 mg/kg/day IV methylprednisolone or equivalent and convert to 1-2 mg/kg/day oral prednisone or equivalent upon improvement.^a • If event resolves to Grade 1 or better, resume atezolizumab.^b • If event does not resolve to Grade 1 or better while withholding atezolizumab, permanently discontinue atezolizumab and contact Sponsor.^c
Immune-related myocarditis, Grade 3-4	
 • Permanently discontinue atezolizumab and contact Sponsor.^c • Refer subject to cardiologist • Initiate treatment as per institutional guidelines and consider antiarrhythmic drugs, temporary pacemaker, ECMO, or VAD as appropriate. • Initiate treatment with 1-2 mg/kg/day IV methylprednisolone or equivalent and convert to 1-2 mg/kg/day oral prednisone or equivalent upon improvement.^{a,b} • If event does not improve within 48 hours after initiating corticosteroids, consider adding an immunosuppressive agent. • If event resolves to Grade 1 or better, taper corticosteroids over >1

ECMO = extracorporeal membrane oxygenation; VAD = ventricular assist device

- Atezolizumab may be withheld for a longer period of time (ie, >12 weeks after event onset) to allow for corticosteroids (if initiated) to be reduced to ≤ 10 mg/day oral prednisone or equivalent. The acceptable length of the extended period of time must be agreed upon by the investigator and the Sponsor.
- If corticosteroids have been initiated, they must be tapered over ≥ 1 month to ≤ 10 mg/day oral prednisone or equivalent before atezolizumab can be resumed.
- Resumption of atezolizumab may be considered in subjects who are deriving benefit and have fully recovered from the immune-related event. Subjects can be rechallenged with atezolizumab only after approval has been documented by both the investigator (or an appropriate delegate) and the Sponsor.

Table 20: Management Guidelines for Dermatologic Events

Event	Management
Dermatologic event, Grade 1	
 • Continue atezolizumab. • Consider treatment with topical corticosteroids and/or other symptomatic therapy (eg, antihistamines).
Dermatologic event, Grade 2	
 • Continue atezolizumab. • Consider subject referral to dermatologist. • Initiate treatment with topical corticosteroids. • Consider treatment with higher-potency topical corticosteroids if event does not improve
Dermatologic event, Grade 3	
 • Withhold atezolizumab for up to 12 weeks after event onset.^a • Refer subject to dermatologist. • Initiate treatment with 10 mg/day oral prednisone or equivalent, increasing dose to 1-2 mg/kg/day if event does not improve within 48-72 hours. • If event resolves to Grade 1 or better, resume atezolizumab.^b • If event does not resolve to Grade 1 or better while withholding atezolizumab, permanently discontinue atezolizumab and contact Sponsor.
Dermatologic event, Grade 4	
 • Permanently discontinue atezolizumab and contact the Sponsor.^c

a. Atezolizumab may be withheld for a longer period of time (ie, >12 weeks after event onset) to allow for corticosteroids (if initiated) to be reduced to ≤ 10 mg/day oral prednisone or equivalent. The acceptable length of the extended period of time must be agreed upon by the investigator and the Sponsor.

b. If corticosteroids have been initiated, they must be tapered over ≥ 1 month to ≤ 10 mg/day oral prednisone or equivalent before atezolizumab can be resumed.

c. Resumption of atezolizumab may be considered in subjects who are deriving benefit and have fully recovered from the immune-related event. Subjects can be rechallenged with atezolizumab only after approval has been documented by both the investigator (or an appropriate delegate) and the Sponsor.

Table 21: Management Guidelines for Neurologic Disorders, Including Meningoencephalitis
